1.3 Number of subjects

Sample size of in total 150 subjects to be enrolled to this study was determined so that at least safety data of 100 subjects treated by ZS as long as one year will be collected, assuming 35% drop out rate.

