4.1.6 Descriptive summary of continuous variables

Descriptive summary of continuous variables includes n, mean, standard deviation (SD), median, minimum and maximum). In the summary of change or percent change from baseline values, 95% confidence interval (95%CI) for the mean (percent) change from baseline will be calculated based on t-distribution.

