4.1.9 Repeated measures mixed model for log-transformed S-K

A longitudinal repeated measures analysis using direct likelihood will be performed. The SAS procedure PROC MIXED will be used. The dependent variable will be the log-transformed S-K values measured post-baseline during the MP. The least square means (LSMeans) and its 95%CIs for each visit (time point) as well as the average over certain period of time will be derived from the model by specifying appropriate contrasts. The model estimates (LSMeans and 95%CIs) will be back transformed to original scale.

The model will include the fixed categorical effect of Visit and fixed continuous covariate of CP baseline S-K, MP baseline S-K and baseline eGFR. Age category (<55, 55-65, >= 65 years) and binary indicators for presence of Heart Failure, CKD, Diabetes and RAASi use will also be included. An unstructured matrix of within-subject error variance covariance will be used. The denominator degrees of freedom will be calculated according to Kenward-Roger method.

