4.2.4 Efficacy

4.2.4.1 Efficacy in the Maintenance Phase

Analysis of S-K related variables

- Proportion of patients who can maintain normokalemia (defined as S-K level of ≥ 3.5 and ≤ 5.0 mmol/L, inclusive) on ZS at each Maintenance Phase study visit

Number (%) of subjects who can maintain normokalemia at each Maintenance Phase study visit and last on treatment visit will be tabulated with binomial proportion and its 95%CI.

- Proportions of patients who were hypokalemic (< 3.5 mmol/L) or hyperkalemic (> 5.0 mmol/L) at each Maintenance Phase visit.

For each visit and last on treatment, patients will be classified to either normokalemic, hypokalemic or hyperkalemic by their S-K value. Number and proportion for each category will be tabulated.

- Observed values at visit and change from baseline in S-K over time

Observed S-K values at each visit/last on treatment and changes from CP baseline and from MP baseline will be summarized by descriptive summary statistics. For changes from baseline, 95%CI will be also presented.

- Subject-level average S-K over certain period of time
- Proportion of patients with average S-K ≤ 5.1 mmol/L
- Proportion of patients with average S-K ≤ 5.5 mmol/L

Average S-K level per subject will be calculated over the certain period of time (as specified in section 3.2.1). Continuous summary statistics will be provided for each. In addition, number (%) of subjects meeting ≤ 5.1 or ≤ 5.5 mmol/L will also be summarized with binomial proportion and its 95%CI.

- Model-based estimates for S-K over time as well as average S-K levels over certain period of time

The log-transformed S-K data will be analysed with mixed model as described in section 4.1.9. All post-baseline data will be included into the model. The LS Mean and 95% CI at each timepoint as well as over certain period of time (as specified in section 3.2.1) will be produced using appropriate contrasts. The estimates and 95% CIs will be back-transformed to original scale and tabulated.

- Number of normokalemic days during Maintenance Phase

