The number of normokalemic days during the MP will be calculated assuming that the time interval between assessments is normokalemic only if both the beginning and end assessments for that time interval display normal S-K values. If an intermediate scheduled assessment time point is missing, then the scheduled assessment is regarded as not normokalemic. In order to determine this variable all scheduled or unscheduled fasting S-K will be taken into calculation. Descriptive statistics and 95% CI for mean for the number of normokalemic days will be provided.

- Change in S-K level from the last on-treatment Maintenance Phase visit to the End of Study

To investigate if S-K increases after stopping treatment, change in S-K from last on-treatment visit to MP EOS (MP follow up) visit will be summarized with continuous summary statistics and 95% CI for mean.

Sensitivity analysis for missing S-K values

For the mean S-K over time, longitudinal repeated measures model specified above will serve as a sensitivity check to missing S-K values. It provides estimates of S-K over time *had subjects remained on ZS for planned 52 weeks* under the Missing At Random assumption.

Further sensitivity analyses may be conducted depending on the volume of missing data as well as on the reason of study discontinuation.

Sensitivity analysis with iSTAT potassium measurements

Since the ZS dose adjustment during study is based on iSTAT measurement, analyses with categorized values (e.g. proportion of subjects with normokalemia) are expected to be sensitive to which of S-K or iSTAT K are analysed.

Summary of Potassium value over time, proportion of subjects with normokalemia and number of normokalemic days will be repeated using iSTAT potassium measurements instead of S-K values provided by Central lab. Only observed iSTAT values measured within last ZS dose + 1 day (+ 2 days on QOD regimen) will be used.

Sensitivity analysis with iSTAT potassium measurements for Correction Phase will be also carried out as outlined in section 4.2.5

Analysis with S-K adjusted for assay change bias

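### The missing-data check on mean S-K compares arithmetic means with geometric means, so its result mixes a change of scale with any effect of missing data

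*SAP*

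**What the plan says.** Section 4.2.4.1 of the SAP describes S-K by visit as follows: "Observed S-K values at each visit/last on treatment and changes from CP baseline and from MP baseline will be summarized by descriptive summary statistics". Section 4.1.6 fixes the content of such a summary: "Descriptive summary of continuous variables includes n, mean, standard deviation (SD), median, minimum and maximum". The mean is therefore arithmetic, and no geometric mean is planned.

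The repeated measures model in section 4.1.9 works on another scale: "The dependent variable will be the log-transformed S-K values measured post-baseline during the MP". Its results are then converted: "The model estimates (LSMeans and 95%CIs) will be back transformed to original scale". No correction to an arithmetic mean is named, and the SAP nowhere calls the converted values geometric means.

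Under the missing-data heading of section 4.2.4.1 the two are linked: "For the mean S-K over time, longitudinal repeated measures model specified above will serve as a sensitivity check to missing S-K values". The SAP says that the model estimates S-K as if all subjects had stayed on ZS for the full 52 weeks, under a missing-at-random assumption. Other missing-data analyses are optional. The same model also supplies the averages over the periods in section 3.2.1, which are reported alongside the subject-level averages.

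**The concern.** A sensitivity analysis for missing data should change the missing-data assumption and keep the estimated quantity fixed. Here both change. The exponential of a mean log is a geometric mean, so model and descriptive summary would disagree even if every subject attended every visit. A reader who compares the two tables cannot tell directly how much of a difference, or of an apparent agreement, comes from missing data.

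This is the only missing-data check on mean S-K to which the SAP commits, in a study planned with 35% drop-out.

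**Working it through.** **Inputs from the SAP.** Section 1.3 plans 150 subjects so that "at least safety data of 100 subjects treated by ZS as long as one year will be collected, assuming 35% drop out rate". Check: 100/0.65 = 153.8, so 154 against the stated 150, which is within 3%; 150 × 0.65 = 97.5 expected completers.

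**Inputs assumed.** The SAP gives no mean or SD for S-K. Its only anchor is normokalemia, "defined as S-K level of ≥ 3.5 and ≤ 5.0 mmol/L, inclusive". Reading that 1.5 mmol/L width as about 4 SD gives an SD near 0.375. The ranges used are mean 4.5 to 5.0 mmol/L, SD 0.3 to 0.7 and n 75 to 150.

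**Offset with complete data.** For lognormal S-K with mean μ, let s² = ln(1 + (SD/μ)²). Then

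arithmetic mean − geometric mean = μ × (1 − exp(−s²/2)) ≈ SD²/(2μ).

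Dividing by SE = SD/√n gives about (SD/μ) × √n/2. Example: μ = 4.7 and SD = 0.5 give 0.25/9.4 = 0.027 by the approximation and 0.0264 exactly. With n = 100, SE = 0.05, so the offset is 0.53 SE.

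Results at μ = 4.7:

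| SD | Offset (mmol/L) | SE units, n = 75 | n = 100 | n = 150 |
|---|---|---|---|---|
| 0.3 | 0.0095 | 0.28 | 0.32 | 0.39 |
| 0.4 | 0.0169 | 0.37 | 0.42 | 0.52 |
| 0.5 | 0.0264 | 0.46 | 0.53 | 0.65 |
| 0.6 | 0.0378 | 0.55 | 0.63 | 0.77 |
| 0.7 | 0.0513 | 0.63 | 0.73 | 0.90 |

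The extremes of the full range are 0.0090 mmol/L and 0.26 SE (μ = 5.0, SD 0.3, n = 75), and 0.0535 mmol/L and 0.94 SE (μ = 4.5, SD 0.7, n = 150). Normally distributed S-K gives nearly the same offset (0.0269 instead of 0.0264 at μ = 4.7, SD 0.5).

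**Period averages.** The offset in mmol/L stays about the same, but averaging within subjects shrinks the SE. Take the whole Maintenance Phase (Visits 7 to 23, 17 visits), with assumed μ = 4.8, SD = 0.5, n = 97 and constant within-subject correlation ρ. Then SE = 0.5 × √((1 + 16ρ)/17)/√97. The offset of 0.0258 is 0.87, 0.70 or 0.60 SE for ρ = 0.3, 0.5 or 0.7.

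**Effect on the check.** A large-sample simulation used two visits, normal S-K, mean 4.7, SD 0.5, correlation 0.5 and no covariates. At the second visit 35% were missing, with higher S-K at the first visit raising the chance of drop-out. Likelihood estimates were computed on both scales.

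| Log-odds of drop-out per SD | Bias of observed mean | Raw-scale model − observed | Back-transformed log model − observed |
|---|---|---|---|
| 0 | 0.000 | 0.000 | −0.027 |
| 0.3 | −0.025 | +0.026 | −0.002 |
| 0.5 | −0.041 | +0.041 | +0.014 |
| 0.8 | −0.061 | +0.061 | +0.033 |
| 1.2 | −0.083 | +0.083 | +0.054 |

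The raw-scale model recovers the bias. The planned comparison is lower by about 0.027 throughout. If subjects with lower S-K left instead, an observed mean too high by 0.025 should give a difference of −0.025. The planned comparison would then show about −0.025 − 0.027 = −0.052, roughly double.

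**The case against.** **Direction is not documented.** A reader might infer that the check hides bias, because drop-out for high potassium is easy to imagine. The SAP does not support that as a general claim. It gives no reasons behind its 35% drop-out, and its Table 1 stops dosing at both ends of the potassium range, including at 3.0-3.4 mmol/L on the lowest dose. The distortion can go either way. This objection stands.

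**No fixed cancellation or SE figure follows.** One could calculate that if the 35% who leave would have been 0.1 mmol/L higher, the bias is 0.35 × 0.1 = 0.035, of which an offset of 0.0258 (mean 4.8, SD 0.5) cancels 74% and one of 0.0371 (SD 0.6) cancels 106%. But the 0.1 has no source. With 0.2 the same offsets cancel 37% to 53%, and with 0.3 they cancel 25% to 35%. Likewise, half a standard error is a central value under assumptions and not a property of the plan. Both points stand.

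**The offset can be estimated from planned output.** The descriptive table has the SD, so SD²/(2 × mean) can be worked out, and under lognormality the median estimates the geometric mean. Early visits, with little drop-out, show the offset almost alone. This holds in part. The SAP does not tell the reader to do it, the median is noisier, and the offset varies with the SD: at mean 4.7 it rises from 0.017 to 0.038 if the SD goes from 0.4 to 0.6. Subjects enter the Maintenance Phase with i-STAT potassium in the normal range, so a narrower spread at early visits is plausible. The offset is not removed.

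**An untransformed model alone may not be enough.** Section 4.1.9 adjusts for age category and four binary indicators without stating how LSMeans are weighted. With equal weights, a factor of 20% prevalence and a 0.1 mmol/L effect (illustrative) shifts the LSMean by (0.5 − 0.2) × 0.1 = 0.03, as large as the scale offset. This stands and is taken into the fix.

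**Conclusion.** The check is not like for like. Followed exactly, the plan compares arithmetic observed means with geometric model means, and the latter are lower even with complete data. The offset is about SD²/(2 × mean), or 0.01 to 0.05 mmol/L and roughly 0.3 to 0.9 SE, over the assumed ranges of mean, SD and n. That the model mean falls below the observed mean on complete data follows from the SAP (covariate weighting aside); the size rests on those assumptions.

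The consequence is that scale and missing-data effects are mixed. The documents do not show that bias will be hidden, nor how much of it.

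Importance is low. The offset is well below the 0.208 mmol/L assay shift in section 4.2.4.1. S-K is a secondary efficacy variable in a single-arm study whose primary variables are safety, and section 4.1.1 makes all analyses descriptive.

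**What to change.** In section 4.2.4.1, under the missing-data heading, add one of the following:

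- fit the section 4.1.9 model also to untransformed S-K and use that fit for the comparison with the observed means; or
- tabulate observed geometric means per visit and period and compare the back-transformed LSMeans with those.

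In either case, state that LSMeans are computed at the observed covariate margins of the FAS-MP, taken over subjects and not over records, so that covariate weighting does not add a second difference unrelated to missing data. Label the back-transformed LSMeans as geometric means wherever they appear. The log model can stay.

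The cost is a short SAP addition and one extra model run or table column. No new data are needed.

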4.2.5 Efficacy in the Correction Phase

- Observed values and change from Correction Phase baseline in S-K

Descriptive summary for observed values and changes from baseline through to 24, 48 and 72 hours post dose as well as last on treatment value will be descriptively summarized.

- Proportion of patients who achieved normokalemia at 24, 48 and 72 hours after start of dosing

Number (%) of patients achieved normokalemia at 24, 48 and 72 hours post dose as well as last on treatment value with its 95% CIs will be provided.

Both analyses will be repeated with iSTAT potassium measurements.

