Throughout all phases of the study, most potassium values will be measured at fasting before taking ZS. Nothing should be taken by mouth except water, coffee or tea, with or without milk and/or sugar, and essential medications, for a minimum of 8 hours prior to the blood collection. Potassium level should be determined by both i-STAT and the Central Laboratory on all occasions. Treatment decisions (eg, dose titration, stopping rules) will be made based on

i-STAT potassium values, as these provide clinical sites with a real-time measurement, according to dose modification rules. Statistical analyses on the study data will in principle be based on S-K values as measured by the Central Laboratory.

Safety and tolerability will be assessed on an ongoing basis. Standard study assessments including blood potassium, clinical chemistry (including calcium, magnesium, sodium, phosphate, creatinine, bicarbonate, and blood urea nitrogen [BUN]), aldosterone, renin and hematology parameters, urinalysis, vital signs, physical examinations, and electrocardiograms (ECGs) will be assessed. All women of childbearing potential will have a urine pregnancy test prior to enrollment and at their End of Study (EOS) visit.

Stopping rules will be implemented to ensure subjects discontinue the study treatment and receive alternative therapy in case of significant hyperkalemia, hypokalemia, arrhythmias, or development of congestive heart failure or end stage renal failure.

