2.1.2 Full analysis sets

All efficacy analyses will be performed using an Intent-to-Treat (ITT) principle based on the full analysis sets.

FAS-CP : For the correction phase (CP), the full analysis set will include all patients that receive at least one dose of ZS during the correction phase and have any post-baseline correction phase S-K values.

FAS-MP : For the subsequent long-term maintenance phase (MP), the full analysis set will include all patients who receive at least one dose of ZS during maintenance phase and have any post-baseline maintenance phase S-K values.

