2.2 Protocol deviations

Protocol deviations will be identified programmatically or manually prior to database lock. Subjects who deviate from important protocol conditions (e.g. selected inclusion/exclusion criteria) will be reported as having important protocol deviations.

Important protocol deviations would include but not limited to:

- Patients who received ZS but did not meet Inclusion/Exclusion criteria
- Patients who received prohibited concomitant medication or non-drug therapy
- Patients who received wrong ZS dose regimen (including incorrect up-/down-titration)
- Study drug compliance < 80% or > 120%.

No protocol deviations will lead to exclude subjects from analysis. All the efficacy analyses will be based on the FAS and all the safety analyses will be based on SAF for each phase.

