3.2 Secondary variables

3.2.1 Efficacy in Maintenance phase

Efficacy of long-term ZS treatment in patients with hyperkalemia will be evaluated by the following efficacy measures:

- Proportion of patients who can maintain normokalemia (defined as S-K level of ≥ 3.5 and ≤ 5.0 mmol/L, inclusive) on ZS at each Maintenance Phase study visit
- Proportion of patients with average S-K ≤ 5.1 mmol/L
- Proportion of patients with average S-K ≤ 5.5 mmol/L
- Proportions of patients who were normokalemic (S-K ≥ 3.5 and ≤ 5.0 mmol/L), hypokalemic (< 3.5 mmol/L), or hyperkalemic (> 5.0 mmol/L) at each Maintenance Phase visit.
- Subject-level average S-K over the certain period of time (as specified below)
 - entire MP [Day 2 to Day 362]
 - Month 3 to Month 12 [Day 82 to Day 362]
 - Day 2 to Month 3 [Day 2 to Day 82]
 - Month 4 to Month 6 [Day 110 to Day 166]
 - Month 7 to Month 9 [Day 194 to Day 278]
 - Month 10 to Month 12 [Day 306 to Day 362]
- Observed values at visit and change from baseline in S-K over time up to Week 52 [Day 362]
- Number of normokalemic days during Maintenance Phase
- Change in S-K level from the last on-treatment Maintenance Phase visit to the End of Study
- Change from baseline in S-Aldosterone over time
- Proportion of patients with normal S-Aldosterone
- Change from baseline in S-Bicarbonate over time
- Proportion of patients with normal S-Bicarbonate
- SF-36 v2 questionnaire

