4. ANALYSIS METHODS

4.1 General principles

The SAS® software, version 9.2 or higher, will be used in order to generate all the statistical outputs.

Unless otherwise specified, all efficacy analyses will be carried out on the FAS and all safety analyses will be based on the SAF, for each study phase (CP or MP).

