4.2.2 Demographics and baseline characteristics

Demographic and other baseline characteristics, including disease-related characteristics will be summarized, using the SAF-CP as well as SAF-MP.

Demographic and baseline characteristics are listed in [Table 4](#). Disease-related common baseline characteristics are listed in [Table 5](#).

Table 4 Demographics

Characteristics	Summarized as	Categories
Sex	Categorical	Male, Female
Age	Categorical and Continuous	<65, >= 65 years <75, >= 75 years
Body Weight	Categorical and Continuous	< 65, >= 65 kg
BMI	Continuous	
Height	Continuous	
Race	Categorical	Asian, Other

Table 5 Disease-related characteristics

Characteristics	Summarized as	Categories
CP Baseline S-K	Categorical and Continuous	< 5.5 mEq/L, 5.5-< 6.0 mEq/L, >= 6.0 mEq/L
Baseline eGFR*	Categorical and Continuous:	<15 mL/min/1.73m2, 15-<30 mL/min/1.73m2 30-<60 mL/min/1.73m2 >= 60 mL/min/1.73m2
Comorbidity – Heart Failure	Categorical	Yes, No
Comorbidity - Diabetes	Categorical	Yes, No
Comorbidity - CKD	Categorical	Yes, No

Characteristics	Summarized as	Categories
RAAS Inhibitor Use	Categorical	Yes, No
Diuretic Use	Categorical	Yes, No
On peritoneal dialysis	Categorical	Yes, No

*eGFR derived by Japan guideline formula;

$$eGFR[\text{mL}/\text{min}/1.73\text{m}^2] = \text{SCr}[\text{mg}/\text{dL}]^{-1.094} \times \text{Age}[\text{years}]^{-0.287} (\times 0.739 \text{ for female})$$

All summaries of continuous characteristics will be based on non-missing observations. For categorical characteristics, percentages will be calculated out of the total number of subjects in the analysis set (ie, each denominator includes the number of subjects with missing/unknown values for the characteristic).

Comorbidities will be based on medical history (ongoing), using the following search criteria:

- HF will be searched by standardised MedDRA query (SMQ) (narrow) “Cardiac failure”.
- DM will be searched by SMQ (narrow) “Hyperglycaemia/new onset diabetes mellitus”.
- CKD will be searched by SMQ (narrow) “Chronic kidney disease”.

Current medications were based on concomitant medication used at the time of 1st dose of ZS, using the following search criteria :

- Current RAASi use will be searched by anatomical therapeutic chemical (ATC) class ‘C09’ or ‘C03DA’
- Current Diuretic use will be ATC class ‘C03’, ‘C02LG’, ‘C07CB’, ‘C09BA’, or ‘C09DA’

Medical history

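### The Correction Phase normokalemia proportion has no baseline condition, so any subject already at 3.5 to 5.0 mmol/L on the central laboratory who stays in range counts as a success

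*SAP*

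**What the plan says.** - **Outcome.** Section 4.2.5 tabulates "Number (%) of patients achieved normokalemia at 24, 48 and 72 hours post dose", together with the last on-treatment value and 95% CIs. It sets no baseline condition. Section 3.2.1 gives the normokalemic range, "defined as S-K level of ≥ 3.5 and ≤ 5.0 mmol/L, inclusive", and section 1.2 uses the same limits in the Correction Phase.
- **Population.** Section 4.1 says that, unless otherwise specified, "all efficacy analyses will be carried out on the FAS". Section 2.1.2 defines FAS-CP as "all patients that receive at least one dose of ZS during the correction phase and have any post-baseline correction phase S-K values". Section 2.2 lists treated subjects who failed the entry criteria as important deviations, then states "No protocol deviations will lead to exclude subjects from analysis".
- **Measurement.** Section 1.2 says "Statistical analyses on the study data will in principle be based on S-K values as measured by the Central Laboratory", while treatment decisions at the site use i-STAT because it reads in real time. Section 4.1.2.1 defines CP baseline S-K as the mean of two values 60 minutes apart on CP Day 1, taken to confirm that the subject qualifies.
- **Baseline table.** Table 5 in section 4.2.2 classes CP baseline S-K as "< 5.5 mEq/L, 5.5-< 6.0 mEq/L, >= 6.0 mEq/L" and also summarises it as a continuous variable.
- **Checks already planned.** Section 4.2.5 reports observed S-K and change from CP baseline, and repeats both CP analyses with i-STAT.

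**The concern.** The CP objective in section 1.1 concerns patients with S-K of at least 5.1 mmol/L. Read against it, achieving normokalemia means moving from above 5.0 into the range 3.5 to 5.0. The rule in section 4.2.5 tests only where the subject is afterwards. A subject who qualified on i-STAT at 5.1, had a central-laboratory baseline of 4.9 and still read 4.9 at 24 hours would be a success with no change on the scale analysed.

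There is no control arm against which such subjects would cancel out. This proportion is the only responder result of the Correction Phase, and section 5 puts CP efficacy into the interim analysis made for regulatory submission. The planned tables would not show how many successes were of this kind.

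**Working it through.** **1. Is there a baseline condition anywhere?** The endpoint (3.2.2, 4.2.5), the default set (4.1), FAS-CP (2.1.2) and the deviation rule (2.2) contain none. The definition of CP baseline (4.1.2.1) is not linked to the responder count. The gap in the text is therefore real.

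**2. How could a subject be normal at baseline?** There are two routes.
- Entry on i-STAT with analysis on the central laboratory. Section 1.2 names dose titration and stopping rules as examples of i-STAT decisions, not entry. Section 4.1.2.1 has qualification and baseline on the dosing day, which fits a real-time device. This is an inference.
- A treated entry violator, whom section 2.2 keeps in.

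Section 4.2.4.1 itself expects normokalemia proportions to depend on whether S-K or i-STAT is analysed.

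**3. The plan's own figure.** The SAP gives no expected CP response rate to reproduce. Its only sample-size figure is 150 enrolled for 100 one-year completers at 35% dropout: 100/0.65 = 153.8, or 154, against 150 (150 × 0.65 = 97.5). That is close, and this point does not depend on it. Below, 150 serves only as an assumed size of FAS-CP.

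**4. Size of the shift.** At a given time point let s be the share with central baseline of 5.0 or below, q the share of those who are in range, and p the share of the others who are in range.

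Reported proportion = (1 − s)p + sq, so shift = s(q − p).

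All three inputs are assumptions. Shift in percentage points with q = 100%:

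| s | p = 40% | p = 60% | p = 80% | p = 90% |
|---|---|---|---|---|
| 5% | 3.0 | 2.0 | 1.0 | 0.5 |
| 10% | 6.0 | 4.0 | 2.0 | 1.0 |
| 20% | 12.0 | 8.0 | 4.0 | 2.0 |

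For example, 0.10 × (1.00 − 0.60) = 0.040. With q = 90% the row for s = 10% becomes 5.0, 3.0, 1.0 and 0.0.

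**5. Against sampling error.** With 150 subjects, s = 10%, p = 60% and q = 100%, there are 15 already normal and 135 others, of whom 81 respond.
- All FAS-CP: (81 + 15)/150 = 64.0%, exact 95% CI 55.8 to 71.7.
- Baseline above 5.0: 81/135 = 60.0%, exact 95% CI 51.2 to 68.3.

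**6. How large might s be?** Simulations required two rounded i-STAT readings of at least 5.1 and counted central baseline means of 5.0 or below. The potassium distribution and the measurement errors are assumed.

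| Assumptions | Central minus i-STAT | s |
|---|---|---|
| Source mean 5.3 to 5.7, SD 0.4, device error SD 0.15 to 0.25 | 0 | 0.5% to 3.8% |
| As above | +0.12 to +0.208 | 0% to 1.0% |
| As above | −0.208 | about 6% to 18% |
| Source mean 5.0 or 5.3, SD 0.5, within-subject SD 0.12, between-method SD 0.10 to 0.20 | 0 | 3.4% to 10.1% |
| As above | −0.1 to +0.2 | 0.3% to 17.2% |

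Letting both methods read the same blood draw, as section 1.2 suggests, lowers these shares. At p = 60% and q = 100%, the zero-bias rows correspond to shifts of 0.005 × 40 = 0.2 points up to 0.101 × 40 = 4.0 points.

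**The case against.** The case against giving this much weight is strong in several respects.

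- **Entry device.** The SAP does not say that entry is decided on i-STAT. Section 4.1.2.1 can be read as saying that the S-K values themselves qualify the subject. Already-normal subjects would then be rare violators. This stands, and it limits the size. It does not supply the missing condition. If entry was on central S-K, the i-STAT repeat is the analysis without an assured hyperkalemic baseline.
- **Planned checks.** If entry was on i-STAT, eligible subjects start hyperkalemic on that scale and the i-STAT repeat is sound for them. Change from CP baseline gives no credit to a subject who does not move. Both are useful, but the central-laboratory proportion stays as it is.
- **Table 5.** A reader might infer that the table conceals these subjects. It does not quite: the continuous summary includes the minimum (section 4.1.6), which would show that at least one exists. It would not show how many.
- **ITT principle.** A proportion in all treated subjects is a legitimate description, and section 2.1.2 adopts that principle. Restricting on a second noisy reading would also drop some subjects whose true potassium exceeded 5.0. This stands against replacing the FAS-CP figure, but not against adding a row.
- **Status.** The endpoint is secondary, and section 4.1.1 declares all analyses descriptive. No test is affected.

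**Conclusion.** The concern holds as a minor point. As written, any FAS-CP subject with a central-laboratory baseline of 3.5 to 5.0 who is still in range at the time point is counted as having achieved normokalemia, and no planned table counts such subjects.

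The shift is s(q − p). It is probably 0 to a few percentage points, illustrated by +2 at s = 5% and +4 at s = 10% with p = 60% and q = 100%. This rests on assumed values of s, p and q; the SAP supports none of them.

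Two stronger readings are not supported.
- **That the CP response is materially inflated, with up to about 18% of subjects affected.** The upper shares require the central laboratory to read lower than i-STAT, which the SAP does not state. Its illustration in section 4.1.5.1, which is hypothetical, has the central value 0.12 mmol/L higher. The 0.208 mmol/L assay subtraction is described under the Maintenance Phase (4.2.4.1), whereas section 4.2.5 plans only an i-STAT repeat.
- **That the error can only flatter the drug.** The shift is upward only when q exceeds p. It vanishes as p approaches q, and a normal starter who leaves the range counts as a failure.

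**What to change.** 1. In section 4.2.5, keep the FAS-CP proportion. Add the number of subjects with central-laboratory CP baseline S-K of 5.0 mmol/L or below, and the proportion achieving normokalemia, with exact 95% CI, among those with CP baseline above 5.0.
2. In the i-STAT repeat, add the same row using the i-STAT baseline.
3. In Table 5, split the lowest class into 5.0 or below, and above 5.0 to below 5.5.

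The cost is a few lines of SAP text and an added row or two per table, with no new data and no effect on any treatment rule. The added row will rest on slightly fewer subjects and may look slightly less favourable. If almost nobody had a baseline of 5.0 or below, it will show that the FAS-CP figure is robust.
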